	
 3. Willing and able to provide 4 blood samples: 
 3.1. just prior to vaccination (V1), 3.2. 14–21 days post vaccination (V2) 3.3. 4–6 months post-vaccination (V3) 3.4. 10-12 months post-vaccination (V4) 4. Has not received influenza vaccine for at least 6 months before enrolment 5. Willing to provide current mobile phone number for SMS reminders
Exclusion Criteria:	
 1. Known contraindication(s) for QIV (e.g. hypersensitivity to vaccine component (including eggs)). 2. Recently (last 7 days) or currently ill or has a fever above 38°C. 3. Cannot recall if they were vaccinated against influenza during more or less than two of the preceding five years. 4. Hypogammaglobulinaemia or immunoglobulin replacement 5. Undergoing immuno-suppressive therapies
Number of Planned Subjects:	360
Investigational products:	FluBlok® FlucelVax® Quad Fluarix® (or equivalent egg-grown QIV)
Safety considerations:	The risk of an adverse event associated with, influenza vaccination, blood collection and collection of nasal swab(s) is low. Any adverse event will be recorded and followed up by the project manager or principal investigator.
Statistical Methods:	
Baseline comparisons: Baseline data will be summarised by vaccination group, with each arm.
 
Analysis of the primary objective: The post-vaccination geometric mean titres (GMT) by vaccination regimen will be compared by using mixed-effects linear regression.

Subgroups:	
 A. Frequently vaccinated (vaccinated during 3-5 of the preceding five years) B. Infrequently vaccinated (vaccinated during 0 or 1 of the preceding five years)

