6.2 SECONDARY OBJECTIVES

6.2.1 SECONDARY OBJECTIVE 1

To estimate whether antibody responses to all 4 vaccine antigens are greatest in participants who received QIV-R and least in participants who received QIV-E, and if this reflects greater cell- to egg-grown antibody titre ratios.

Corresponding outcomes:

1. Post vaccination trend in GMT QIV-R > QIC-C > QIV-E
2. Post-vaccination seropositivity and trend in seropositivity of QIV-R > QIC-C > QIV-E
3. Pre- to post-vaccine mean fold-rise in GMT (~ Geometric Mean Ratio (GMR)) and trend in fold rise of QIV-R > QIC-C > QIV-E
4. Post-vaccination seroconversion and trend in the proportion who have seroconverted of QIV-R > QIC-C > QIV-E

6.2.2 SECONDARY OBJECTIVE 2

To estimate whether QIV-R induces antibodies against a greater genetic and antigenic range of A(H3N2) viruses than QIV-C and QIV-E.

Corresponding outcomes:

1. Breadth of antibodies induced by vaccination as measured through pre-vaccination, post-vaccination and post-season serum samples tested against a landscape panel of approximately 30 influenza A(H3N2) strains that have circulated since 1968.

6.2.3 SECONDARY OBJECTIVE 3

To estimate whether prior vaccination history has less effect on antibody responses induced against all 4 vaccine antigens by QIV-R compared with QIV-C and QIV-E.

Corresponding outcomes:

For each vaccine type and vaccination history group (frequently versus infrequently vaccinated) compare:

1. Post-vaccination GMT
2. Post-vaccination seropositivity
3. Post-vaccination fold-rise in geometric mean antibody titre (GMT)
4. Post-vaccination seroconversion fraction
5. Post-vaccination antibody breadth (proportion of landscape antigens with GMT>40)

6.2.4 SECONDARY OBJECTIVE 4

To estimate whether antibody titres against all 4 vaccine antigens are better maintained up to 12 months after vaccination with QIV-R compared with QIV-C and QIV-E

Corresponding outcomes:

1. Post-season GMT
2. Post-season seropositivity
3. Proportion of landscape antigens (as per Objective 2) with GMT>40 post-season

6.2.5 SECONDARY OBJECTIVE 5

To estimate whether QIV-R induces higher frequencies of HA reactive B cells and/or B cells with different HA cross-reactivity profiles and phenotypes compared with QIV-C and QIV-E.

Corresponding outcomes:

1. Heterogeneity of antibody generating B cells in terms of phenotype and reactivity against a panel of well-defined recombinant hemagglutinin probes that represent a range of influenza A(H3N2) virus clades.

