8.4 BLOOD COLLECTION

Participants will be requested to provide blood samples at 4 time-points:

1. Pre-vaccination at Screening or V1 (D-28 to D1)
2. Post-vaccination at V2 (D14 [+7 days])
3. Post-season at V3 (D150 [+/-30 days])

Study Name: Immunogenicity trial of 3 influenza vaccine [VAP3]

Protocol Number: 2021.247

DSRB Ref Number: 2022/00275

Version & date: version 2.0, dated 27 Oct 2022

Page 19 of 38

4. Post-vaccination at V4 (D330+/-30 days), and prior to receiving the following years annual vaccination,

Blood collection will take place at the study sites. At each visit blood samples will be taken from a vein in the arm. Up to 30mls of blood will be drawn. This will always include 10ml in serum tubes, and for 1/3 of participants (20/arm) will also include 20ml in Sodium Heparin tubes. The serum tubes will be processed at the IDRL at NCID and will consist of centrifuging serum tubes to separate sera from clotted blood. Sodium Heparin tubes will be processed at A*Star Infectious Disease labs with whole blood leukocyte subsets analysis on NA Heparin blood, followed by separation of plasma and peripheral blood mononuclear cells (PBMCs). Sera and plasma will be stored at -20°C and four aliquots of PBMCs per sample will be stored in liquid nitrogen. Stored samples will be shared between NCID and WHOCCRRRI.

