The trend will be determined using the estimate of the effect of the cell vaccine and the estimate of the effect of the recombinant vaccine for each of these outcomes. The expected trend is the cell vaccine producing better outcomes than the egg vaccine (estimate of the effect of the cell vaccine should positive) and the recombinant vaccine producing better outcomes than the cell vaccine (the difference of estimates of the effect of recombinant and cell vaccines should be positive).

13.4.3 SECONDARY OBJECTIVE 2

To estimate whether QIV-R induces antibodies against a greater genetic and antigenic range of A(H3N2) viruses than QIV-C and QIV-E.

The breadth of antibodies induced by vaccination will be measured using pre-vaccination and post-vaccination serum samples tested against a landscape panel of approximately 30 influenza A(H3N2) strains that have circulated since 1968. A metric for response breadth (e.g., the proportion of viruses with post/pre vaccination titre ratio of at least 4) will be calculated for each individual and compared using linear regression as for secondary objective 1.

13.4.4 SECONDARY OBJECTIVE 3

To estimate whether prior vaccination history has less effect on antibody responses induced against all 4 vaccine antigens by QIV-R compared with QIV-C and QIV-E.

All analyses for objective 1 and 2 will be repeated including a covariate to indicate the vaccination history group (0=in frequently vaccination; 1=frequently vaccinated). An interaction term between vaccine received and prior vaccination will be included to allow vaccine effect to vary by history of vaccination. Infrequently vaccinated is defined as 0 or 1 prior vaccinations; frequently vaccinated is defined as 3 or more prior vaccinations with any influenza vaccine.

13.4.5 SECONDARY OBJECTIVE 4

To estimate whether antibody titres against all 4 vaccine antigens are better maintained up to 12months after vaccination with QIV-R compared with QIV-C and QIV-E

Post-season log-titres and seropositivity will be compared the same way post-vaccination log-titres and seropositivity are compared in objective 1.

Post-season response breadth will be using the same methods described for objective 2.

13.4.6 SECONDARY OBJECTIVE 5

To estimate whether QIV-R induces higher frequencies of HA reactive B cells and/or B cells with different HA cross-reactivity profiles and phenotypes compared with QIV-C and QIV-E.

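### Objective 4 asks about titres up to 12 months, but its analyses are written for the post-season visit (V3, at most about 6 months), and no estimate of change from V2 is planned

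*Combined protocol and SAP*

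**What the plan says.** - **Objective (synopsis, 6.2.4, 13.4.5).** The question is whether titres against the four vaccine antigens are "better maintained up to 12 months after vaccination with QIV-R compared with QIV-C and QIV-E".
- **Outcomes (6.2.4).** There are three: post-season GMT, post-season seropositivity, and "Proportion of landscape antigens (as per Objective 2) with GMT>40 post-season".
- **Analyses (13.4.5).** "Post-season log-titres and seropositivity will be compared the same way post-vaccination log-titres and seropositivity are compared in objective 1"; and "Post-season response breadth will be using the same methods described for objective 2".
- **Method carried over (13.4.2).** Log-titre change from pre-vaccination is compared between vaccines by linear regression, and seropositivity at one time point by logistic regression. Section 13.4 adds vaccination history as a covariate.
- **Visit labels (8.4).** "Post-vaccination at V2 (D14 [+7 days"; "Post-season at V3 (D150 [+/-30 days"; "Post-vaccination at V4 (D330+/-30 days), and prior to receiving the following years annual vaccination". The synopsis places the last sample at "10-12 months post-vaccination (V4".
- **Testing (10.1).** Pre-vaccination, post-vaccination and post-season sera are tested against the vaccine strains. Visit numbers are not given.

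**The concern.** The objective has a 12-month horizon, and a blood sample is taken near 12 months. Yet the only label used in the outcomes and analyses belongs, in the one section that ties it to a visit, to the sample at about 5 months. If the plan is followed literally, the V4 titres have no analysis. If it is followed loosely, someone must decide later whether the outcome is V3, V4, both or a pooled value, possibly with the data in hand.

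The second issue concerns the word *maintained*. The planned comparisons use the late level, or the change from V1. The trial's main hypothesis is that QIV-R gives a higher response after vaccination. If it does, and all vaccines then wane at the same rate, QIV-R is still higher at V3. That result could be reported as better maintenance although waning did not differ, and no planned interval would show this.

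**Working it through.** **1. Visit timing, from the windows in 8.4 at 30.44 days per month**

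| Visit | Label in 8.4 | Days | Months | Stated in 11.1 |
|---|---|---|---|---|
| V2 | post-vaccination | 14–21 | 0.5–0.7 | 14–21 days |
| V3 | post-season | 120–180 | 3.9–5.9 | 4–6 months |
| V4 | post-vaccination | 300–360 | 9.9–11.8 | 10–12 months |

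The stated month ranges are reproduced. The latest V3 sample (Day 180) and the earliest V4 sample (Day 300) are 120 days apart, so V3 cannot stand in for V4. Only V4 reaches the objective's horizon.

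**2. Where V4 titres could enter.** Section 10.1 may cover V4 testing, because 8.4 labels V4 post-vaccination. Section 13.4 names neither V4 nor 12 months in any titre analysis. Section 13.4.6 compares B cells at each time point, but that is not a titre analysis.

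**3. What the planned comparison shows under equal waning.** The inputs are the A(H3N2) design values in 13.3: b_R = 0.5, b_C = 0.25, and b_R-add = 0.2 in the frequently vaccinated (or 0 as a simpler case). With equal strata, b_R-add contributes 0.2/2 = 0.1 on average. Let every vaccine fall by the same factor f between V2 and V3. On the underlying log scale:

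- change from V1, QIV-R minus QIV-E: (0.5 to 0.6 − ln f) − (0 − ln f) = 0.5 to 0.6, whatever f is;
- change from V1, QIV-R minus QIV-C: 0.25 to 0.35, whatever f is;
- change from V2, QIV-R minus either comparator: 0.

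The late comparison therefore returns the peak difference. Only the change from V2 bears on waning. With complete data, the V3 coefficient minus the V2 coefficient gives its point estimate. The interval also needs their covariance or the participant-level data, and neither contrast nor interval is planned.

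**4. How the added contrast behaves.** Simulation used the 13.3 model and titre intervals, with titres below 10 set to 5 as 13.3 describes. There were 54 participants per cell (60 less 10%), and the model contained vaccine and vaccination history. Simulating the plan's own power table with the same model gave 0.796 one-sided and 0.695 two-sided at 55 per cell, against 0.810 and 0.712 stated. Two inputs are assumptions, because the documents give neither: an equal fall in all arms, and added V2-to-V3 variance of 0.1 to 1.

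| Assumed equal fall | Two-sided 5% rejection of equal waning, QIV-R vs QIV-E |
|---|---|
| up to 1.5-fold | near 5% |
| 3-fold | about 8–11% |
| 5-fold | about 14–28% |

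The bias runs against QIV-R: −0.01 to −0.08 log versus QIV-E for falls of 1.5- to 3-fold. More QIV-E titres reach the floor, so their fall is understated. Versus QIV-C the bias is 0 to −0.05 log, and rejection stays at about 4–6% over the same falls. The 95% CI half-width is 0.12 to 0.27 log.

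**5. How far these falls go.** At the mean baseline of 3.7, the design values give QIV-E a rise of 1.1 + 0.8 × 3.7 − 3.7 = 0.36 log (1.43-fold) in the infrequently vaccinated. In the frequently vaccinated it is 0.36 − 0.2 = 0.16 log (1.17-fold). The average is 0.26 log. A 1.5-fold fall (0.41 log) already puts mean QIV-E about 0.15 log below its pre-vaccination level. The 3- and 5-fold rows are stress cases for the floor, not forecasts.

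**The case against.** **A labelling slip.** Section 13.4 gives no visit numbers for titres, so the link from post-season to V3 rests on one list in 8.4. That list looks loose: it calls V4 post-vaccination, while 4.2.1 ties the post-vaccination GMT to 14–21 days. The 12-month horizon stands directly above the post-season sentence in 13.4.5, and V4 is timed before the next annual vaccine. It is plausible that post-season was meant to cover both late visits. This stands as a possibility, and it limits the claim to what the text says. It does not remove the need for the change: even on that reading the plan does not say whether V3, V4 or both is the outcome.

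**A choice of estimand.** Section 6.2.4 defines maintenance through late GMT, seropositivity and breadth, and 13.4.5 analyses those. Late level is a legitimate measure, and the missing interval can be computed from data already collected. This stands. The change from V2 therefore belongs beside the level outcomes as a supporting estimate and should not replace them.

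**Stronger readings a reader might infer.** One is that a significant late difference under equal waning is a false positive. It is not: the levels really differ, and the chance of detecting that difference is power, not an error rate. Another is that V4 sera will go untested. Section 10.1 leaves that open.

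**Conclusion.** The point holds as a gap between the objective and its analysis. As written, a 12-month question is answered with samples from at most about 5.9 months. The V4 titres have no assigned analysis. The planned comparisons cannot tell slower waning from a higher peak. The first two conclusions rest only on the labels in 8.4, 6.2.4 and 13.4.5. The third follows from the form of the comparison and needs no assumed waning rate.

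The documents do not support saying that the planned level comparisons are invalid, or that the authors meant to leave V4 out. The simulated rejection rates concern the added contrast, not the current plan. They depend on the assumed falls, and they show why titres below 10 need proper handling if that contrast is used.

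This is a secondary objective. The primary analysis, sample size and power figures do not change. The correction should be made, and it is cheap.

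**What to change.** 1. Give V3 and V4 distinct labels in 8.4, 6.2.4 and 10.1, and name both visits in 13.4.5.
2. Keep GMT, seropositivity and breadth as the Objective 4 outcomes, reported at V3 and at V4 and described as persistence of level.
3. Add, as a supporting estimate, the between-vaccine difference (QIV-R vs QIV-E and QIV-R vs QIV-C) in V2-to-V3 and V2-to-V4 log-titre change, with 95% CI. A repeated-measures model with vaccine, visit, vaccine-by-visit, vaccination history and baseline log-titre would provide it. Treat titres below 10 as left-censored in the main fit, not only in a sensitivity analysis.
4. State that a difference in late level alone will not be described as slower waning.

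The cost is wording in four sections and a modest amount of extra analysis. V4 blood is already collected, so no visit or draw is added. V4 HI assays are an extra cost only if they were not already budgeted.

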10.5 B CELL ANALYSIS

PBMC will be thawed and stained with up to four fluorescent labelled recombinant HA probes representing the vaccine strain and prior A(H3N2) vaccine strains, together with monoclonal antibodies against B cell activation and differentiation markers and isotypes (IgG, IgG3, IgM, IgA, IgD). Stained samples will be analysed on a five laser Cytek Aurora. The magnitude of total HA-reactive B cell response and HA cross-reactivity profiles will be compared.

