13.4 STATISTICAL ANALYSES

Study Name: Immunogenicity trial of 3 influenza vaccine [VAP3]

Protocol Number: 2021.247

DSRB Ref Number: 2022/00275

Version & date: version 2.0, dated 27 Oct 2022

Page 31 of 38

The stratification variable of vaccination history will be included as a covariate in models for all primary and secondary objectives.

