The percentage of B memory phenotype (CD27+ and/or IgD-) cells that are HA probe reactive on d14 will be estimated for each vaccine arm, accounting for pre-vaccination percentage and vaccination history as described in 13.3. The HA probe cross-reactivity, isotype, and phenotype of HA reactive B cells for each vaccine group and time-point will be visually compared using t-distributed stochastic neighbor embedding (t-SNE), a statistical method for visualizing high-dimensional data by giving each datapoint a location in a two or three-dimensional map.

13.4.7 SECONDARY OBJECTIVE 6

To assess whether QIV-R offers better protection against infection compared with QIV-C or QIV-E.

Evidence of influenza infection will be based on RT-PCR-confirmed infection, only, as serological evidence may be biased in vaccinees who elicit a good antibody response to vaccination (22).

Attack rates will be calculated for each vaccination group as the number of cases during the person-time at risk. If there are sufficient cases, the proportion testing positive for each vaccine will be compared using logistic regression with influenza infection as 1 if test-positive and 0 if test-negative or not tested and no ARI. The explanatory variable will be the type of vaccine (1=QIV-R, 2=QIC-C, 3=QIV-E). Samples size permitting, we will also explore whether attack rates were associated with the post-vaccination GMT.

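### Section 13.4.6 compares B-cell cross-reactivity, isotype and phenotype between vaccines only by eye on t-SNE maps, so the profile part of Objective 5 gets no estimate or interval

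*Combined protocol and SAP*

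**What the plan says.** Objective 5, as restated in section 13.4.6, has two parts. One concerns the frequency of HA-reactive B cells. The other concerns "B cells with different HA cross-reactivity profiles and phenotypes compared with QIV-C and QIV-E". Section 6.2.5 lists a single outcome: "Heterogeneity of antibody generating B cells in terms of phenotype and reactivity against a panel of well-defined recombinant hemagglutinin probes".

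Section 13.4.6 treats the two parts differently:

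- **Frequency.** "The percentage of B memory phenotype (CD27+ and/or IgD-) cells that are HA probe reactive on d14 will be estimated for each vaccine arm", with allowance for the pre-vaccination percentage and vaccination history in the manner of section 13.3.
- **Profiles.** At every visit and in every vaccine group, the features of the HA-reactive cells (probe cross-reactivity, isotype, phenotype) "will be visually compared using t-distributed stochastic neighbor embedding", which the same sentence describes as "a statistical method for visualizing high-dimensional data".

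The laboratory description in section 10.5 says: "The magnitude of total HA-reactive B cell response and HA cross-reactivity profiles will be compared". It gives no metric, model or interval. The general rule at the start of section 13.4 is: "The stratification variable of vaccination history will be included as a covariate in models for all primary and secondary objectives".

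**The concern.** An objective worded as an estimate of whether profiles differ between vaccines needs a quantity that can differ, an estimate of the difference, and a measure of its uncertainty. A t-SNE display supplies none of these. It places cells, not participants, on a map. Side-by-side maps carry no between-participant error and make no adjustment for baseline values or the stratification factor.

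The part left to the eye is not incidental. It corresponds to the only outcome listed in 6.2.5, and it bears on Hypothesis 4 in section 5.2, that a higher antigen dose induces new B-cell responses alongside recalled memory. Cross-reactivity between the vaccine-strain probe and the probes for prior A(H3N2) vaccine strains (section 10.5) is direct evidence on that. As planned, the finding would be a judgement about how maps look, and the features to be remarked on could be chosen after the maps are seen.

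**Working it through.** The plan states no figure for this analysis, so there is none to reproduce. The check has two parts.

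**1. Does any section supply a quantitative comparison of the profiles?**

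| Place | What it contributes |
|---|---|
| 6.2.5 | Names heterogeneity as the outcome; no metric |
| 10.5 | Announces a comparison of profiles; no metric, model, test or interval |
| 13.4, opening rule | Requires vaccination history as a covariate in models; no model is named for the profiles, so the rule does not reach them |
| 13.4.6 | A model for the frequency; visual comparison for cross-reactivity, isotype and phenotype |
| 13.4.3 (Objective 2) | For antibody breadth, a metric per individual compared by linear regression; not extended to B cells |

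None does, and no section labels the profile part descriptive or exploratory. Objective 2 shows that the plan already uses the needed approach for a similar question about breadth.

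**2. Could the planned subset support a quantitative comparison?**

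Inputs:
- Section 9.2 sets a target of 20 in each of 6 groups: 6 × 20 = 120 participants, or 2 × 20 = 40 per vaccine.
- Section 8.4 gives one third of participants: 360 / 3 = 120, which agrees. It also writes this as 20 per arm. Over three vaccine arms that would be 3 × 20 = 60, which fits one third only if arm there means each of the 6 groups.
- The documents give no SD for any B-cell measure, so results are in SD units.
- Two-sided 5% and 80% power are assumed for illustration; section 13.2 sizes the trial on the primary objective only.

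Formulas for one pairwise contrast with n per vaccine, no baseline adjustment and no interaction terms:
- smallest detectable difference = (1.96 + 0.84) × √(2/n)
- 95% interval half-width = 1.96 × √(2/n)

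| n per vaccine | √(2/n) | Detectable difference | Half-width |
|---|---|---|---|
| 40 (20 × 2 strata) | 0.224 | 2.80 × 0.224 = 0.63 SD | 1.96 × 0.224 = 0.44 SD |
| 36 (40 less 10%) | 0.236 | 2.80 × 0.236 = 0.66 SD | 1.96 × 0.236 = 0.46 SD |
| 20 (literal 20 per arm) | 0.316 | 2.80 × 0.316 = 0.89 SD | 1.96 × 0.316 = 0.62 SD |

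The 10% loss is borrowed from section 13.2; no loss rate is given for the subset. Adjustment for the pre-vaccination value could narrow the intervals. The model in 13.3 includes vaccine-by-history interactions. If these are kept, the QIV-R coefficient alone describes the infrequently vaccinated stratum, with 20 per vaccine, and the last row applies to it.

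**The case against.** The strongest defence is that displaying high-dimensional flow data descriptively is a respectable choice for a secondary, mechanistic objective in a one-third subset. The outcome is called heterogeneity, the trial is sized on the primary objective alone, and the frequency endpoint is modelled. This stands as an argument for keeping t-SNE and for treating the point as minor. It does not remove the mismatch with an objective worded as estimation, because the plan does not call this part descriptive.

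A reader might also infer several stronger things that the documents do not support:

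- **That Objective 5 as a whole has no proper analysis.** The HA-reactive percentage is modelled with baseline and vaccination history taken into account.
- **That the percentage is analysed off the log scale used for titres.** Section 13.4.6 refers to 13.3 and neither states nor excludes a transformation. The scale is unspecified, no more.
- **That a few participants with many cells would dominate the maps.** The plan does not say how cells are sampled per participant. This is possible, but it is an assumption, and the point does not need it.
- **That the extra blood is wasted.** The heparin tubes also serve the modelled frequency, leukocyte subsets and plasma (8.4), the B-cell characterisation under Objective 6, and, with consent, future research (14.1.1.3).

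It is also fair to object that replacing the maps with many shares creates a multiplicity problem. Section 10.5 lists five isotype markers; with QIV-R against two comparators, those alone give 5 × 2 = 10 contrasts at one visit. Shares of exactly zero or one, which can occur when few HA-reactive cells are recovered, also break a log or logit scale. Both objections stand, and the fix has to deal with them.

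**Conclusion.** The point holds for the profile part of Objective 5 only. For cross-reactivity, isotype and phenotype, section 13.4.6 specifies a visual comparison that cannot yield a between-vaccine estimate or interval, and no other section fills the gap. This is an inexpensive improvement to a secondary objective; the primary analysis and the frequency endpoint are untouched.

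The figures of 0.63 SD at 40 per vaccine and 0.89 SD at 20 describe what a quantitative analysis could detect. They do not measure bias or lost power in the present plan. They apply to one unadjusted contrast at two-sided 5% with 80% power. The value at 40 rests on reading the subset as 20 in each of 6 groups, which section 9.2 and the one-third fraction in 8.4 both support. A quantitative comparison is feasible, with precision suited to moderate or large differences.

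**What to change.** In section 13.4.6:

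1. Name in advance a small set of per-participant summaries: for example, the share of HA-reactive B cells that cross-react with the prior A(H3N2) vaccine-strain probes, plus a few key isotype and phenotype shares.
2. Compare arms at day 14 with a model of the 13.3 type, adjusting for the pre-vaccination value and vaccination history. State the scale, the handling of shares of zero or one, and whether the interaction terms are kept.
3. Report differences with 95% confidence intervals. Either apply a multiplicity rule or state that the intervals are unadjusted and exploratory.
4. Keep t-SNE as illustration.
5. State the scale for the percentage of HA-reactive memory B cells.

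Sections 8.4 and 9.2 should also use the same unit for the subset of 20. If the sponsor prefers to keep the profiles visual, the minimum is to label that part descriptive and reword the objective to match.

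The cost is a little more programming and analysis, with no extra blood or assays. The downside is several secondary comparisons of limited precision.
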